2 IDENTIFICATION AND DESCRIPTION OF THE INVESTIGATIONAL DEVICE

Manufacturer	GI View Ltd.
Model/Type	Aer-O-Scope Colonoscope System (MASA 0101-0202)
Traceability	Work station will be identified by Catalog number and serial number. Aer-O-Scope Disposable Scanner will be identified by serial number and lot number.

Clinical Investigational Plan			
Protocol ID	934CLD	Sponsor	GI View Ltd.
Revision	03	Investigational Device	Aer-O-Scope® Colonoscope System

	Released software will be identified by SW number and revision. All systems will be traced using a specific device traceability form in accordance with GI View SOP 690CLP Device Inventory and Accountability or equivalent ISO 14155:2011 compliant SOP from the company's CRO.
Intended Purpose	
The Aer-O-Scope Colonoscope System is intended to provide panoramic (360°) visualization (via a video monitor) and diagnostic/therapeutic access to the adult lower gastrointestinal tract, (including but not limited to, the anus, rectum, sigmoid colon, transverse colon, cecum and ileocecal valve) for endoscopy.
 
The Aer-O-Scope Scanner (colonoscope component of the Aer-O-Scope System) is a single use, disposable device. The Aer-O-Scope Scanner cannot be reprocessed.

Populations	The Aer-O-Scope Colonoscope System is intended for adult populations indicated for screening, diagnostic (minor complaints such as rectal bleeding or minor abdominal pain) or polyp surveillance colonoscopy.
Investigational Device Description	
The Aer-O-Scope Colonoscope System provides panoramic (360°) visualization (via an external video monitor) and diagnostic/therapeutic access to the adult lower gastrointestinal tract for endoscopy (including but not limited to, the anus, rectum, sigmoid colon, transverse colon, cecum and ileocecal valve). The system has two main components:
 
 • The Aer-O-Scope Workstation – Facilitates the operation of the Aer-O-Scope Disposable Scanner. This includes supply and control over CO₂, water, suction, air pressure, and the power supply for the camera and illumination. The Aer-O-Scope Workstation receives and processes data sent to and from the Aer-O-Scope Disposable Scanner including pneumatic controls, video signals from the camera and the pressure measurements utilized by the Aer-O-Scope propulsion system to manage navigation within the colon. The Workstation features an ergonomic joystick for the control of the Aer-O-Scope Disposable Scanner optical imaging head steering to streamline navigation. • The Aer-O-Scope Disposable Scanner – Is the colonoscope component of the System. The Aer-O-Scope Disposable Scanner is a single-use, self-propelled device that incorporates a CMOS chip that facilitates the introduction of the highly sophisticated visualization system, featuring 360° panoramic omni-view capabilities. The scanner moves through the entire colon and into the cecum. The Scanner captures high-resolution video images of the colon mucosa, transmitted in real-time, to the workstation and then video monitor and is digitally recorded for future reference. The propulsion mechanism uses a series of soft pliable polyurethan balloons and CO₂ gas to propel the optical imaging head into and then out of the colon. Two working channels for the provision of therapeutic access are incorporated in the scanner. The Scanner is disposable and cannot be reprocessed.
Training	For the purpose of this study, the operators will be expert GI endoscopists. Each operator will undergo 2-3 day(s) of training including didactic

Clinical Investigational Plan			
Protocol ID	934CLD	Sponsor	GI View Ltd.
Revision	03	Investigational Device	Aer-O-Scope® Colonoscope System

	
presentations regarding the operation of the Aer-O-Scope. Hands on experience operating the system in a model will also be provided prior to initiating the study. Training procedures for general operation of the system will be included in up to the first ten (10) procedures in the study – the exact number to be determined by the physician’s perceived proficiency based on a Likert Scale questionnaire. Up to the first twenty (20) therapeutic interventions will be considered therapeutic training procedures – the exact number to be determined by the physician’s perceived proficiency based on a Likert Scale questionnaire. Up to the first 10 training procedures will not be analyzed in the final statistical analysis for polyp visualization.

Medical Procedure	
The Aer-O-Scope Disposable Scanner like any conventional colonoscope is inserted into the rectum and then maneuvered to the cecum. The Aer-O-Scope has an incorporated propulsion system to advance the optical imaging head through the colon. The propulsion system utilizes soft pliable balloons and CO₂ gas to gently propel the optical imaging head inwards on intubation and outwards upon retraction. The operator gently eases the multi-luminal cable inward towards the cecum during the insertion phase and gently pulls the cable during retraction scan phase both while steering the optical imaging head with the ergonomic joystick.
 
If pathology of any type is detected during the procedure, a standard therapeutic accessory (at least 230cm in length and ≤1.8mm in diameter) is inserted through one of the Aer-O-Scope two (2) working channels (2.1mm diameter each) and the polyp is removed or biopsied. In the event that the pathology cannot be removed due to size, shape and/or location, the area adjacent to the pathology is tattooed to mark for later therapeutic intervention.
 
In this study, subjects will undergo tandem colonoscopy with the Aer-O-Scope Colonoscope System and a conventional colonoscope (see Appendix 2: Conventional Colonoscopes Used in this Investigation). Subjects will be randomized in blocks to begin either with the Aer-O-Scope Colonoscope System or with the conventional colonoscope. The same endoscopist will perform both procedures. Because the physicians will see which device they are using to perform the colonoscopies, blinding will not be possible.
 
Each subject will undergo colonoscopy in tandem with each device. All pathologies will be removed (or tattooed) during the procedures.
 
Data will be documented on Case Report Forms (973CLD). Data related to adenomas will be retrieved from histology reports.

Clinical Investigational Plan			
Protocol ID	934CLD	Sponsor	GI View Ltd.
Revision	03	Investigational Device	Aer-O-Scope® Colonoscope System

3 JUSTIFICATION FOR THE DESIGN OF THE CLINICAL INVESTIGATION

Pre Clinical Testing/ Assessment	
This post marketing study is intended to demonstrate the ability to better visualize colonic abnormalities using the Aer-O-Scope Colonoscope System.
 
During the course of the last decade, several major visualizations studies have been performed and it has become common practice to use the “second-pass” method for determining visualization methods^{ii,iii,iv}. This study is intended to demonstrate a significantly lower adenoma miss rate using the Aer-O-Scope Colonoscope System as compared to a conventional colonoscope.
 
GI View performed a comparative visualization study in swine during the course of 2013 and 2014 and demonstrated a superior ability to visualize pathologies as compared to an Olympus CF140L colonoscope v.
 
GI View performed an ex vivo study using harvested swine colons with implanted pseudo-polyps to demonstrate the ability of the Aer-O-Scope Colonoscope System to provide therapeutic access for therapeutic interventions.
 
Following an extensive review of the published biomedical literature, GI View designed this study to be the same as similar studies in the published literature.
 
The population in this study is the same population indicated for screening, diagnostic and surveillance colonoscopy as seen in the published professional literature. A list of articles can be found in Appendix 4: Bibliography.

---	---

4 INVESTIGATIONAL DEVICE AND CLINICAL INVESTIGATION RISKS & BENEFITS

Risks	
The risks associated with the Aer-O-Scope Colonoscope are similar to those risks associated with conventional optical colonoscopy. As with all procedures related to colon screening, there are some associated risks. Risks associated with both colonoscopy and the Aer-O-Scope Colonoscope may include but are not limited to the following:
 
 • Lower digestive tract bleeding, • Colon perforation (that may result in inflammation of the peritoneum (peritonitis) or need for emergency medical treatment), • Excessive insufflation of the colon, • Erosion of the colon mucosa, • Sepsis • Venous thrombosis, • Vasovagal events, • Pain, • Ano-rectal Fissures, • Bloating and • Discomfort. 
Anticipated adverse device effects include bloating, flatulence mild in nature, ano-rectal fissures and minor discomfort. These symptoms are all transient and do not pose a potential risk to the subjects’ health.
 
The Aer-O-Scope Colonoscope system has been designed to minimize

--------------	---

Clinical Investigational Plan

Protocol ID	934CLD	Sponsor	GI View Ltd.
Revision	03	Investigational Device	Aer-O-Scope® Colonoscope System

	these adverse effects.
Benefits	
Colonoscopy is the gold standard for colon inspection and is a safe and effective procedure. Previous studies of colonoscopy have proven beneficial in the prevention of colon cancer. The Aer-O-Scope Colonoscope may allow a simpler and faster examination, potentially resulting in increased capacity and thus shorter waiting periods for the colon examination.
 
The Aer-O-Scope Colonoscope's unique video system with both forward and omni-directional (360° panoramic) cameras allows greater visualization of the colon both in front and behind the colonic folds as compared to conventional forward-viewing colonoscopy. This was demonstrated in the comparative animal study. A higher detection rate has been shown to lead to lower rates of interval cancers.
 
In addition, the Aer-O-Scope Colonoscope Disposable Scanner is a single use device. As such, each subject receives a new, unused, clean device, eliminating the risk of infectious disease transmission from improper or inadequate high level disinfection. This also reduces the amount of toxic chemicals needed for high-level disinfection.
 
The Aer-O-Scope Colonoscope design is intended to potentially lower the risk of colonic perforation by using a soft and very flexible multi-lumen cable – rather than the more rigid tube used with standard colonoscopes. This design has the potential for substantially reducing the risk of colonic perforation, which can be life threatening.

Clinical Investigational Plan			
Protocol ID	934CLD	Sponsor	GI View Ltd.
Revision	03	Investigational Device	Aer-O-Scope® Colonoscope System

5 HYPOTHESES OF THE CLINICAL INVESTIGATION

Hypotheses	
1. Primary Hypotheses:
 
1.1. Colonoscopy with the Aer-O-Scope Colonoscope System will have lower AMR than the conventional forward-viewing colonoscopes. The mean adenoma miss rate for conventional colonoscopy as found in the published literature is between 15-40%.
 
The number missed adenomas (NMA) (based on histology) for each of the two cohort groups in back-to-back tandem colonoscopy will be measured.
 
The NMA is defined as the number of adenomas (based on histology) detected during the second pass colonoscopy that were not detected and removed (or tattooed) during the first pass colonoscopy.
 
The AMR will be measured by the NMA divided by the total number of adenomas detected (for each cohort).
 
1.2. Colonoscopy with the Aer-O-Scope Colonoscope System is safe for screening, diagnostic and surveillance colonoscopy.
 
2. Secondary Hypotheses:
 
2.1. Colonoscopy with the Aer-O-Scope Colonoscope System will have a lower PMR than the conventional forward-viewing colonoscopes.
 
The number missed polyps (NMP) for each of the two cohort groups in back-to-back tandem colonoscopy will be measured.
 
The NMP is defined as the number of polyps detected during the second pass colonoscopy that were not detected and removed (or tattooed) during the first pass colonoscopy.
 
The PMR will be measured by the NMP divided by the total number of adenomas detected (for each cohort).
 
2.2. Colonoscopy with the Aer-O-Scope Colonoscope System will have lower AAMR than the conventional forward-viewing colonoscopes.
 
The number missed advanced adenomas (NMAA) (based on histology) for each of the two cohort groups in back-to-back tandem colonoscopy will be measured.
 
The NMAA is defined as the number of advanced adenomas (based on histology) detected during the second pass colonoscopy that were not detected and removed (or tattooed) during the first pass colonoscopy.
 
The AAMR will be measured by the NMAA divided by the total number of adenomas detected (for each cohort). Because approximately only 6% of all adenomas are considered advanced adenomas, the evaluation of this objective will most likely not

-------------------	--

Clinical Investigational Plan			
Protocol ID	934CLD	Sponsor	GI View Ltd.
Revision	03	Investigational Device	Aer-O-Scope® Colonoscope System

	
reach statistical significance due to the small expected sample size of advanced adenomas.
 
2.3. Physicians will be proficient in operation of and visualization with the Aer-O-Scope Colonoscope System within the first ten (10) cases. Perceived proficiency will be measured using the five (5) point Likert Scale shown below. Physicians will be asked to grade their performance proficiency of intubation, maneuverability, scanning (withdrawal) and visualization using the Aer-O-Scope Colonoscope System throughout the study. For the purpose of this study, the Likert Scale will be used only for Aer-O-Scope colonoscopies.
 
Physicians will be proficient in the achievement of therapeutic access for the purpose of therapeutic interventions within the first 20 therapeutic interventions (per physician). Perceived proficiency will be measured using the five (5) point Likert Scale shown below. Physicians will be asked to grade their performance proficiency of tool insertion, maneuverability and ability to perform therapeutic intervention via the Aer-O-Scope colonoscope. For the purpose of this study, the Likert Scale will be used only for the Aer-O-Scope colonoscopies. An overall score between 1 and 3 will be considered proficient.
 
  
 LIKERT SCALE	USABILITY	
   
 1	Easy to perform	
 
 2	Slightly complicated to perform	
 
 3	Neutral (Neither easy nor difficult)	
 
 4	Complicated to perform	
 
 5	Very Complicated to perform	
  
 
2.4. Colonoscopy timing with the Aer-O-Scope Colonoscope System and conventional forward-viewing colonoscopes will be documented for data collection only for the following properties:
 
2.4.1. Time to cecal intubation – procedures will be timed using a stopwatch. The time spent on therapeutic interventions will be deducted from the intubation time. The Aer-O-Scope and conventional colonoscopes will be equivalent.
 
2.4.2. Withdrawal time - procedures will be timed using a stopwatch. The time spent on therapeutic interventions will be deducted from the withdrawal time. The Aer-O-Scope and conventional colonoscopes will be equivalent.
 
2.4.3. Total procedure time – The total procedure time will be recorded from initial intubation through final retraction. The time spent on therapeutic interventions will be deducted from the overall time. The Aer-O-Scope and
	LIKERT SCALE	USABILITY	1	Easy to perform	2	Slightly complicated to perform	3	Neutral (Neither easy nor difficult)	4	Complicated to perform	5	Very Complicated to perform
LIKERT SCALE	USABILITY												
1	Easy to perform												
2	Slightly complicated to perform												
3	Neutral (Neither easy nor difficult)												
4	Complicated to perform												
5	Very Complicated to perform												

Clinical Investigational Plan			
Protocol ID	934CLD	Sponsor	GI View Ltd.
Revision	03	Investigational Device	Aer-O-Scope® Colonoscope System

	conventional colonoscopes will be equivalent.
Claims and Performance	The Aer-O-Scope Colonoscope System will have a lower overall number of missed adenomas as compared with conventional forward-viewing colonoscopy. An interim analysis will be performed upon completion of each study site.
Risks and Adverse Effects	All serious adverse events and unexpected adverse events as well as adverse device effects will be evaluated in the course of this study.

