Study Objectives	
1. Primary Objectives:
 
1.1. To measure the adenoma miss rate (AMR) (based on histology) for the Aer-O-Scope colonoscopy as compared to the AMR for conventional colonoscopy in a tandem back-to-back study.
 
The AMR is defined as the percentage of adenomas missed per cohort (either by the Aer-O-Scope colonoscope or a conventional colonoscope) and is measured by the number of missed adenomas (detected in the second pass colonoscopy) divided by the total number of adenomas detected per cohort.
 
See Number of Subjects above for cohort group definitions
 
1.2. To demonstrate the Aer-O-Scope Colonoscope System is safe for the performance of screening, diagnostic (minor cases such as rectal bleeding and/or abdominal pain) and polyp surveillance colonoscopy.
 
2. Secondary Objectives:
 
2.1. To measure the polyp miss rate (PMR) for the Aer-O-Scope colonoscopy as compared to the PMR for conventional colonoscopy in a tandem back-to-back study.
 
The PMR is defined as the percentage of polyps missed per cohort (either by the Aer-O-Scope colonoscope or a conventional colonoscope) and is measured by the number of missed polyps (detected in second pass colonoscopy) divided by the total number of polyps detected per cohort.
 
(See Number of Subjects above for cohort group definitions).
 
2.2. To measure the advanced adenoma (≥10mm with villous histology or with high grade dysplasia based on histology) miss rate (AAMR) for the Aer-O-Scope colonoscopy as compared to the AAMR for conventional colonoscopy in a tandem back-to-back study.
 
The AAMR is defined as the percentage of advanced adenomas missed per cohort (either by the Aer-O-Scope colonoscope or a conventional colonoscope) and is measured by the number of missed advanced adenomas (detected in second pass colonoscopy) divided by the total number of polyps detected per cohort.

Clinical Investigational Plan

Protocol ID	934CLD	Sponsor	GI View Ltd.
Revision	03	Investigational Device	Aer-O-Scope® Colonoscope System

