	
It should be noted that the expected number of advanced adenomas will be significantly lower than the number of polyps and the number of adenomas. The evaluation of this objective will most likely not reach statistical significance due to the small expected sample size of advanced adenomas.
 
2.3. To define and document the learning curve for the operation of the Aer-O-Scope Colonoscope System and use of therapeutic access using the Aer-O-Scope Colonoscope System – Using a 5 point Likert Scale (for perceived physician proficiency). The first ten (10) cases will be training for system operation. The first twenty (20) therapeutic interventions per physician will be training for therapeutic access.
 
2.4. Colonoscopy timing for both Aer-O-Scope and conventional colonoscopy will be documented for the following properties:
 
2.4.1. Cecal intubation time (not including therapeutic intervention times)
 
2.4.2. Withdrawal time (not including therapeutic intervention times)
 
2.4.3. Total procedure time (not including therapeutic intervention times)
 
3. Tertiary Objectives:
 
3.1. Timing of therapeutic interventions (see Appendix 3: Therapeutic Accessories Used in This Study) performed with the Aer-O-Scope Colonoscope System will be documented for the purpose of data collection only

Study Endpoints	
1. Primary
 
1.1. Adenoma miss rates (AMR) for each study cohort
 
1.2. No serious adverse events or serious adverse device effects using the Aer-O-Scope Colonoscope System.
 
2. Secondary
 
2.1. Polyp miss rates (PMR) for each study cohort
 
2.2. Advanced adenoma miss rates (AAMR) for each study cohort
 
2.3. Perceived proficiency in Aer-O-Scope operation, mean Likert score between 1-3.
 
2.4. Cecal intubation time (not including therapeutic intervention times)
 
2.5. Withdrawal times (not including therapeutic intervention times)
 
2.6. Total procedure time (not including therapeutic intervention times)
 
3. Tertiary
 
3.1. Therapeutic intervention metrics (time, tool, success rate)

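### PMR is divided by polyps in the synopsis but by adenomas in Section 5, and AAMR has two conflicting denominators, neither of them the number of advanced adenomas

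*Combined protocol and SAP*

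**What the plan says.** **PMR.** Synopsis (Section 1.5), Secondary Objective 2.1, in words: "The PMR is defined as the percentage of polyps missed per cohort". Its formula agrees with the words: "number of missed polyps (detected in second pass colonoscopy) divided by the total number of polyps detected per cohort". Section 5, Secondary Hypothesis 2.1, gives a different formula: "The PMR will be measured by the NMP divided by the total number of adenomas detected (for each cohort".

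**AAMR.** Synopsis, Secondary Objective 2.2, in words: "The AAMR is defined as the percentage of advanced adenomas missed per cohort". Its formula does not match: "number of missed advanced adenomas (detected in second pass colonoscopy) divided by the total number of polyps detected per cohort". Section 5, Secondary Hypothesis 2.2, gives a third version: "The AAMR will be measured by the NMAA divided by the total number of adenomas detected (for each cohort". The same paragraph adds that "approximately only 6% of all adenomas are considered advanced adenomas".

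**Test.** Section 7 assigns a two-sided 5% two-proportion Z-test to both AMR and PMR, and makes rejection of the null the pass criterion. It names no test for AAMR. It gives no denominator for either rate and does not refer back to Section 1.5 or Section 5. Section 6.2 defines a missed polyp and a missed adenoma but gives no PMR or AAMR denominator.

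**The concern.** A miss rate is the share of lesions of a given type that the first pass failed to find, so the lesions counted in the numerator must all be counted in the denominator. The Section 5 PMR breaks this rule: missed non-adenomatous polyps are counted above the line and left out below it. The result is a ratio of two different counts. It moves with the histological mix as well as with visualization, and it has no upper bound of 1. The Z-test's binomial variance does not describe it.

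The AAMR formulas have the opposite fault. The numerator is contained in the denominator, but the denominator is filled with lesions that are not advanced, so the figure can never exceed the share of lesions that are advanced.

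Two analysts following two sections of the same plan would therefore report different PMR and AAMR values from the same data. The trial is unblinded and has an interim analysis as each site completes, so the choice of denominator should not be left until data have been seen.

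**Working it through.** The documents state no PMR or AAMR value, so there is no figure of the plan's own to reproduce. The check compares the definitions and then sizes the difference.

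**Step 1. Definitions side by side**

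| Rate | Numerator | Denominator, synopsis | Denominator, Section 5 | Denominator implied by the name |
|---|---|---|---|---|
| AMR | missed adenomas | adenomas | adenomas | adenomas |
| PMR | missed polyps | polyps | adenomas | polyps |
| AAMR | missed advanced adenomas | polyps | adenomas | advanced adenomas |

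Only AMR is consistent.

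**Step 2. Inputs**

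From Section 7: 240 patients, 10% dropout, 50% of patients with adenomas, 2 adenomas each, expected AMR 0.10 and 0.25. From Section 5: 6% of adenomas advanced. Not in the documents, hence assumed: adenoma share of polyps f = 50-70%, and true PMR p = 10-25% (the two AMR values borrowed for illustration).

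Expected adenomas: 240 × 0.9 = 216 patients; 216 × 0.5 × 2 = 216 adenomas, or 108 per cohort. Advanced: 216 × 0.06 ≈ 13. Polyps per cohort: 108/0.7 ≈ 154 or 108/0.5 = 216.

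**Step 3. AAMR if every advanced adenoma is missed (true rate 100%)**

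- Section 5: 13/216 ≈ 6.0%.
- Synopsis: 0.06 × f, which is 3.0% at f = 50% and 4.2% at f = 70%.

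**Step 4. PMR as Section 5 reports it: p / f**

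- True 10%: 0.10/0.7 = 14.3%; 0.10/0.5 = 20.0%.
- True 25%: 0.25/0.7 = 35.7%; 0.25/0.5 = 50.0%.

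Histological mix alone can create a difference. A true PMR of 25% in both cohorts reads 0.25/0.5 = 50.0% in one and 0.25/0.6 = 41.7% in the other if their adenoma shares are 50% and 60%.

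**Step 5. Effect on the Z-test**

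The test treats the ratio as a binomial proportion on the adenoma count. The actual variance, divided by that binomial variance, is:

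- adenoma count random, same expected mix in both cohorts: (1 − 2p + p/f) / (1 − p/f)
- adenoma count fixed and equal: (1 − p) / (1 − p/f)

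At p = 10%, f = 70% these are 0.943/0.857 = 1.10 and 0.900/0.857 = 1.05. At p = 25%, f = 50% they are 1.00/0.50 = 2.00 and 0.75/0.50 = 1.50. The false-positive rate is about 2 × [1 − Φ(1.96/√ratio)]: 6.2% to 16.6% with random counts, and 5.6% to 11.0% with fixed counts.

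Simulation agrees (400,000 trials per setting; polyp total fixed, lesions independent, missing unrelated to histology, same miss probability in both cohorts, pooled two-sided test at 1.96):

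| f | True PMR | Section 5, random adenoma count | Section 5, 108 adenomas fixed |
|---|---|---|---|
| 70% | 10% | 6.2% | 5.7% |
| 70% | 17.5% | 7.5% | 6.3% |
| 70% | 25% | 9.1% | 7.1% |
| 50% | 10% | 8.1% | 6.5% |
| 50% | 17.5% | 11.6% | 8.4% |
| 50% | 25% | 16.9% | 10.7% |

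With polyps as denominator the rate is 4.9-5.1% in all six settings.

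**The case against.** The strongest reply is that this is a copying slip whose intent is plain. The Section 5 PMR sentence mirrors the AMR sentence above it with the numerator changed. The synopsis has PMR right in words and in formula, Section 6.2 defines detected polyps next to missed polyps, and a two-proportion test only makes sense with polyps below the line. For PMR this is a fair reading of intent, but no text gives the synopsis precedence over Section 5. For AAMR it does not help, because neither formula is right. The synopsis remark that significance is unlikely "due to the small expected sample size of advanced adenomas" shows which lesions were meant, but it does not correct the formula.

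Other points that stand as limits:

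- The inflated error rate arises only if Section 5 is followed. About 17% is the worst corner of an assumed grid.
- A ratio above 1 needs a true PMR above the adenoma share, which does not happen in the range examined.
- If the devices truly differ by 25% against 10%, the denominator hardly changes the chance of rejection: 94.5% (Section 5, random adenoma counts) against 94.3% (polyps) at a 70% share, and about 99% either way at 50%.
- AAMR has no named test, significance is already disclaimed, and the ratio between cohorts is broadly kept if lesion mix is similar.
- Section 6.1 replaces some withdrawn patients, so up to 240 rather than 216 may complete. That changes counts, not the percentages in Steps 3 and 4.

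None of these removes the contradiction.

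**Conclusion.** The concern holds. The definitions of two secondary endpoints contradict each other in current text. Following Section 5 for PMR, or either section for AAMR, produces a figure that is not the miss rate it is named for. PMR matters more because it is formally tested. Under Section 5 it is overstated by a factor of 1/f (1.4 to 2.0 at the assumed shares), and the 5% test rejects about 6-17% of the time under no difference with random adenoma counts, or 6-11% with equal fixed counts. The size rests on the assumed share, the borrowed miss rates and independent lesions. The direction does not rest on the share: the variance is understated whenever some polyps are not adenomas. For AAMR the harm is in reporting, since a complete failure to find advanced adenomas would appear as 6.0%, or 3.0-4.2% under the synopsis.

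This should be fixed, but it does not threaten the main result: AMR is defined consistently and the sample size of 240 does not depend on these formulas.

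**What to change.** - Section 5, Secondary Hypothesis 2.1: PMR = missed polyps / all polyps detected in both passes in the cohort.
- Synopsis, Secondary Objective 2.2, and Section 5, Secondary Hypothesis 2.2: AAMR = missed advanced adenomas / all advanced adenomas detected in both passes in the cohort.
- Section 7: refer to these definitions for PMR and AAMR.

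The cost is three sentences and one cross-reference, to be settled before the first site-level interim analysis. Little or no new data is needed, because Section 6.2 already sends each removed polyp to histology as its own specimen. Lesions tattooed and never removed may lack study histology. A count of them beside AAMR would be useful but is optional.

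The correction restores the nominal level only for independent lesions. Clustering of lesions within patients is a separate matter that it does not address.

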7 STATISTICAL CONSIDERATIONS

Measurements	The pass criteria for the study objectives are rejecting the Null hypotheses as presented below.
Primary Hypothesis:	Colonoscopy with the Aer-O-Scope Colonoscope System will have lower AMR than the conventional forward-viewing colonoscopes.
Statistical Analysis Assumptions:	
 The Adenomas rate within the sample will be 50% (see Appendix 4: Bibliography). The adenoma rate in the sample, for patients with Adenomas, will be 200% (average of 2 adenomas per person). (see Appendix 4: Bibliography) The differences in AMR between the two groups will be 15% (see Appendix 4: Bibliography) The expected AMR of the two groups will be 0.10 vs 0.25 (see Appendix 4: Bibliography) The drop-out rate will be 10%.
Statistical Analysis Plan: Hypotheses testing based calculations	
 For testing the hypothesis that the Aer-O-Scope Colonoscope System will have lower AMR and PMR than the conventional forward-viewing colonoscopies we will perform the Z-tests for comparing two proportions. The tests will be two-sided with significant level of 5%. To demonstrate the physicians proficiency in operation of (including therapeutic interventions) and visualization with the Aer-O-Scope Colonoscope descriptive statistics will be performed using the Likert Scale questionnaire. A mean score between one (1) and three (3) will denote proficiency.
Sample Size Calculation:	The sample size calculation based on the independence AMR between the two groups. A total of 240 patients are needed to compare the AMR between the groups using Z-test for two proportions comparisons. This number enables a 10% dropout, and does not include 70 patients (20-30 training subjects per site (sub-investigator dependent) for learning qualification. This sample size based on a significant level of 5% and a power of 80% to prove a difference in AMR between the groups.

Clinical Investigational Plan			
Protocol ID	934CLD	Sponsor	GI View Ltd.
Revision	03	Investigational Device	Aer-O-Scope® Colonoscope System

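### The proficiency scale for secondary endpoint 2.3 is out of order (2 is harder than 3), so the mean 1–3 rule can pass a harder set of ratings and fail an easier one

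*Combined protocol and SAP*

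**What the plan says.** Section 5, hypothesis 2.3, defines a five-point scale with these labels: 1 *Easy*, 2 "Slightly complicated to perform", 3 "Neutral (Neither easy nor difficult" (the label closes with a bracket), 4 *Complicated*, 5 *Very Complicated*.

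For operation of the system: "Physicians will be asked to grade their performance proficiency of intubation, maneuverability, scanning (withdrawal) and visualization". That is four items, rated throughout the study. For therapeutic access there are three: tool insertion, maneuverability and ability to perform the intervention.

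The threshold appears in three places:

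- Section 5: "An overall score between 1 and 3 will be considered proficient".
- Section 1.5, secondary endpoint 2.3: "Perceived proficiency in Aer-O-Scope operation, mean Likert score between 1-3".
- Section 7: "A mean score between one (1) and three (3) will denote proficiency", with descriptive statistics as the analysis.

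The Training row of section 2 also makes the number of training procedures depend on "perceived proficiency based on a Likert Scale questionnaire".

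**The concern.** A task that is slightly complicated lies on the difficult side of neutral. Read by their words, the labels run in the order 1, 3, 2, 4, 5. Because the rule averages the numeric codes, the misplaced label feeds directly into the verdict: each *Slightly complicated* rating pulls the mean down by one point relative to a *Neutral* rating, although it reports more difficulty.

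At stake is whether the stated criterion for a listed secondary endpoint means what it says. There is also an interpretation problem. If some physicians follow the words and others follow the numbers, the same score means different things and a pooled mean cannot be read.

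**Working it through.** **Inputs.** The codes 1 to 5 and their labels, and the four operation and three therapeutic items, come from section 5. The rule, mean at or below 3, comes from sections 1.5, 5 and 7. Equal weighting of items, and application of the rule to one set of ratings, are assumptions; the documents do not say how the overall score is formed. The plan gives no figure of its own to reproduce here.

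**Step 1: the printed scale alone.** Mean = sum of codes / number of ratings.

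| Ratings | Mean | Verdict |
|---|---|---|
| 3 *Slightly complicated* + 1 *Complicated* | (2+2+2+4)/4 = 2.50 | proficient |
| 3 *Neutral* + 1 *Complicated* (easier) | (3+3+3+4)/4 = 3.25 | not proficient |
| 1 *Slightly complicated* + 1 *Complicated* | (2+4)/2 = 3.0 | proficient |
| 1 *Neutral* + 1 *Complicated* (easier) | (3+4)/2 = 3.5 | not proficient |
| 5 *Slightly complicated* + 5 *Complicated* | (10+20)/10 = 3.0 | proficient |
| 9 *Neutral* + 1 *Complicated* (easier) | (27+4)/10 = 3.1 | not proficient |

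In each pair the harder set passes and the easier one fails. This result needs no view on which correction was intended.

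**Step 2: how many inversions exist.** Order the labels by their wording (*Easy*, *Neutral*, *Slightly complicated*, *Complicated*, *Very Complicated*). Take every pair of rating sets of equal size in which one is at least as hard as the other throughout, after sorting, and harder somewhere. Count the pairs where the harder set passes and the easier one fails.

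| Ratings per set | Ordered pairs | Inversions, printed codes | Inversions, codes in word order |
|---|---|---|---|
| 1 | 10 | 0 | 0 |
| 2 | 90 | 1 | 0 |
| 3 | 455 | 5 | 0 |
| 4 | 1694 | 13 | 0 |

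**Step 3: effect if labels 2 and 3 were transposed.** Exchange codes 2 and 3 and compare verdicts over all unordered rating sets.

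- Four items: 70 sets. The verdict changes in 10: 5 from proficient to not, 5 the other way. For example, 3 *Slightly complicated* + 1 *Complicated* goes from 2.50 to (3+3+3+4)/4 = 3.25, and 3 *Neutral* + 1 *Complicated* goes from 3.25 to (2+2+2+4)/4 = 2.50.
- Three items: 35 sets. The verdict changes in 4: 2 each way.

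**Step 4: where nothing changes.** All *Slightly complicated* gives 2.0 as printed and 3.0 exchanged, proficient both ways; all *Neutral* gives 3.0 and 2.0, also proficient both ways. Any set made only of codes 1 to 3 has a mean of at most 3 under either coding. A change therefore requires at least one 4 or 5.

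**The case against.** The strongest reply accepts the label order and disputes its weight.

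- **The counts in step 3 apply to only one repair.** If label 2 is a wording slip for a category between easy and neutral, the codes are already right and no recorded number changes its verdict. This stands: 10 of 70 and 4 of 35 are conditional on transposition. The printed-scale comparison in step 1 does not depend on the repair.
- **Physicians may use the scale as a numeric gradient and ignore the words.** Such raters would be unaffected. This also stands as a limit, but the labels are the only meaning the protocol gives to the scores.
- **The mean may pool many cases rather than the items of one case.** True; the documents do not settle it. Pooling does not remove the inversion, as the ten-rating example shows.
- **The cutoff absorbs much of the disorder, since both disputed labels lie within 1 to 3.** True, as step 4 shows.
- **The endpoint is descriptive, with no test, comparator or alpha.** True, and it caps the importance. The endpoint nevertheless carries an explicit threshold, which needs an ordered scale.
- **The physicians' questionnaire may be worded correctly.** Possibly. It is not reproduced; section 2 says only that data are recorded on case report form 973CLD. Section 5, however, says proficiency is measured with the scale it prints.

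**Conclusion.** The concern holds as a minor point. The anchors are out of order as printed, and the proficiency rule can return opposite verdicts to those the words imply when ratings of 2 or 3 are mixed with 4s or 5s. This assumes that physicians rate by the labels and that ratings are averaged with equal weight. The documents give no distribution of ratings, so how often it would happen is unknown.

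No error rate, power figure or sample size is affected. An effect on which cases enter the visualization analysis is possible, because up to the first ten training procedures are left out and the questionnaire helps set their number. It is not shown, because the Training row does not say that the mean 1–3 rule ends training. I give it no weight.

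**What to change.** The sponsor should confirm what was intended, then either reword label 2 as a *slightly easy* category or exchange labels 2 and 3. Either makes the scale monotone. The section 5 table should be reconciled with the questionnaire the physicians actually complete (case report form 973CLD, if it is held there). One sentence should say how any ratings already given under the printed labels will be handled, for example by reporting the distribution over labelled categories instead of a mean.

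The cost is one or two labels and one sentence. It follows the amendment route in section 9 (agreement of the sponsor, the coordinating investigator and all principal investigators, then distribution to investigators and the ethics bodies) and can travel with any other amendment. It is best done before the scale is used, since ratings given under ambiguous labels cannot be reliably recoded.
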